3.5. Safety Endpoints

Safety endpoints will be summarized based on the on-treatment period unless otherwise specified.

The on-treatment period is defined as the time from the first dose of study intervention through the minimum of 90 days after last dose, or (start day of new anticancer therapy - 1 day). Anticancer therapy includes drug therapy and radiation with curative intent; the start of new anticancer therapy after the first dose of study intervention is derived as outlined in [Section 5.2.6](#). Adverse events occurring on the same day as the first dose of study intervention will be considered to have occurred during the on-treatment period. All other assessments which occur on the same day as the first dose of study intervention will be considered baseline assessments (see [Section 3.4](#) for the definition of baseline).

Safety data collected after the on-treatment period as described above will be listed but not summarized.

3.5.1. Adverse Events

An adverse event (AE) is considered treatment-emergent relative to the study intervention if the event start date is during the on-treatment period (including on the date of first dose).

AEs will be characterized by type, severity, timing, seriousness, and relationship to study intervention.

AEs (except CRS and ICANS) will be graded by the investigator according to the NCI CTCAE version 5.0. CRS and ICANS will be graded according to the ASTCT criteria.¹ All AEs will be coded using the most current version of MedDRA.

TEAEs leading to dose interruption (prior to protocol amendment 2) will be derived from the exposure CRF (dose adjustment reason as adverse event and actual dose taken of 0 for interruption and >0 for reduction) and then linked programmatically to the adverse event CRF by the AE identifier.

3.5.2. Laboratory Data

Hematology and chemistry results will be programmatically graded according to the NCI CTCAE version 5.0 for relevant parameters. A shift summary of baseline grade by maximum postbaseline grade will be presented. Parameters which cannot be graded will be summarized relative to the normal range (ie, normal range high or normal range low). Additional details are provided in [Section 6.8.3](#).

4. ANALYSIS SETS (POPULATIONS FOR ANALYSIS)

For purposes of analysis, the following analysis sets are defined:

Participant Analysis Set	Description
Safety Analysis Set	All enrolled participants who receive at least 1 dose of study intervention.
DLT Evaluable Analysis Set	All enrolled participants in Part 2A and Part 2C, who received the planned 2 doses of 116 mg or 152 mg of study intervention during the DLT observation period or who received at least 1 dose of 116 mg or 152 mg of study intervention and experience DLT(s) during the DLT observation period.
CCI	[REDACTED]
	[REDACTED]
PK Analysis Set	The PK analysis set is a subset of the safety analysis set and will include participants who have at least 1 postdose concentration measurement.
Immunogenicity Analysis Set	All participants in the safety analysis set who have at least 1 sample tested for ADA.
CCI	[REDACTED]
	[REDACTED]

Note: "Enrolled" means a participant's, or his or her legally authorized representative's, agreement to participate in a clinical study following completion of the informed consent process and was assigned to treatment. Potential participants who are screened for the purpose of determining eligibility for the study, but do not participate in the study, are not considered enrolled, unless otherwise specified by the protocol.

5. GENERAL METHODOLOGY AND CONVENTIONS

5.1. Hypotheses and Decision Rules

5.1.1. Hypotheses and Sample Size

5.1.1.1. Primary Endpoint

A Bayesian dual-criterion design⁶ will be used to estimate the primary endpoint of the true Grade ≥ 2 CRS rate during Cycle 1. With this design, the following criteria are defined:

- Bayesian statistical significance: Substantial evidence that the true Grade ≥ 2 CRS rate exceeds a pre-specified value. For this study, Bayesian statistical significance will be achieved if the posterior probability of the true Grade ≥ 2 CRS rate exceeding 35% is $<10\%$;
- Clinical relevance: The maximum number Grade ≥ 2 CRS events threshold that could justify further clinical development. For this study, it is defined as the median of the posterior distribution of the true Grade ≥ 2 CRS rate is $\leq 27\%$.

The analysis will use a Beta-binomial model (binomial sampling for number of Grade ≥ 2 CRS events and a beta prior distribution). A minimally informative beta prior distribution of the true Grade ≥ 2 CRS rate will be used. It is assumed a priori that the true mean Grade ≥ 2 CRS rate is 35%, so the prior distribution will be Beta (0.7, 1.3). Using this prior and based on the dual criteria defined above, approximately 76 participants will be enrolled and treated and a maximum of 20 participants with Grade ≥ 2 CRS events is allowed to meet the dual criteria in 76 participants. If exactly 20 participants in 76 participants experience Grade ≥ 2 CRS events, the observed Grade ≥ 2 CRS rate is 26.3% with median 26.3% and 90% credible interval of (18.7%, 35.0%) based on the posterior distribution.

5.1.1.2. Part 2A and Part 2C

In Part 2A and Part 2C, approximately 8 participants will be enrolled and treated at each dose level to ensure at least 6 DLT evaluable participants (as defined in [Section 4](#)) to be evaluated during the DLT observation period. If any participant is deemed non-evaluable for DLT, additional participants may be enrolled to ensure there are a sufficient number of evaluable participants at each dose level.

CCI

5.1.2. Decision Rules

5.1.2.1. Primary Endpoint

The study is designed to have an interim analysis for futility and a primary analysis. The interim analysis will be conducted once 30 participants in Part 1 either complete Cycle 1 of study intervention or discontinued the study intervention prior to the end of Cycle 1. The primary analysis will be conducted once all participants have completed Cycle 1 of study intervention or have otherwise discontinued the study intervention.

[Table 2](#) presents the operating characteristics of this 2-stage design, ie, the probability of early trial termination at the interim futility analysis and the probability of observing the critical number of Grade ≥ 2 CRS (ie, ≤ 20 participants with Grade ≥ 2 CRS events in 76 participants) at the primary analysis if the true Grade ≥ 2 CRS rate is 20%, 21%, 22%, 23%, 27% and 35%, respectively. For example, if the true Grade ≥ 2 CRS rate = 22%, the probability of stopping the study due to futility at the interim analysis is 0.048, and the probability of observing ≤ 20 participants with Grade ≥ 2 CRS rate at the primary analysis is 0.835.

Table 2. Operating Characteristics of Bayesian 2-Stage Dual-Criterion Design

True Grade ≥ 2 CRS Rate	Prob of Exceeding Futility Boundary at the Interim ($R1/N1 \geq 11/30$)	Prob of GO Decision at the Primary Analysis* ($R/N \leq 20/76$)	Prob of No-GO Decision at the Primary Analysis ($R/N > 20/76$)
20%	0.026	0.919	0.055
21%	0.036	0.882	0.082
22%	0.048	0.835	0.116
23%	0.064	0.779	0.157
27%	0.161	0.488	0.351
35%	0.492	0.065	0.443

* The study does not meet futility criteria at the interim analysis and continues to the primary analysis.

CRS = cytokine release syndrome;

R1 = Number of participants with Grade ≥ 2 CRS events at the interim futility analysis to stop the study for futility;

N1 = Number of participants at the interim analysis;

R = Number of participants with Grade ≥ 2 CRS events to meet the dual criteria at the primary analysis;

N = Number of participants at the primary analysis.

At the time of the primary analysis, the critical number of participants with Grade ≥ 2 CRS events to be observed will be updated based on the actual number of participants enrolled and treated.

5.1.2.2. Part 2A and Part 2C

A BLRM will be utilized for dose determination. The dosing decision and estimation of the RP2D of elranatamab will be guided by the estimation of the posterior probability of DLT in the DLT observation period. Other evidence such as safety data beyond DLT window, clinical activity, PK, and PD data will also be evaluated in determining RP2D.

As this study uses premedication and a dose regimen with 2 step-up priming doses, which were not used in the Phase 1 study of the same compound (C1071001), there is issue of exchangeability between the historical data and the current design. Therefore, weakly informative priors with weighted mixture prior structure are used for the prior distribution of the BLRM parameters.

After each dosing cohort of participants completes the DLT observation period, the posterior distribution for the risk of DLT for each dose level will be evaluated. The posterior distributions will be summarized to provide the posterior probability that the risk of DLT lies within the following intervals.

- Underdosing: [0, 0.16);
- Target toxicity: [0.16, 0.33);
- Excessive toxicity: [0.33, 1].

Dosing decisions are guided by the EWOC principle.⁷ A dose level may only be used for the next dosing cohort of participants if the risk of excessive toxicity ($[0.33, 1]$) at that dose level is less than 25%.

Table 3 shows some hypothetical dose escalation data scenarios and the corresponding recommendations for the next dose for Part 2A. For example, in Scenario 1, if 1 participant experiences a DLT out of 6 DLT-evaluable participants at 116 mg Q2W dose level, the recommendation is to escalate to the next dose level (152 mg Q2W) with probability of overdosing of 0.083 at 152 mg dose level. In Scenario 3, if 3 participants experience DLTs out of 6 DLT-evaluable participants at 116 mg Q2W dose level, the dose level is deemed too toxic, and the dose finding process will stop with no RP2D identified.

Table 3. Data Scenarios, Next Dose Recommendation, and the Interval Probability of Target Toxicity and Overdosing at Next Dose

Scenarios	Elranatamab Dose Evaluated (mg;)	D/N	Elranatamab Next Dose (mg)	Pr(TT) at Next Dose	Pr(OD) at Next Dose
1	116 Q2W	1/6	152 Q2W	0.362	0.083
2	116 Q2W	2/6	116 Q2W	0.461	0.161
3	116 Q2W	3/6	N/A	N/A	N/A
4	152 Q2W 116 Q2W	1/6 0/6	152 Q2W	0.199	0.010
5	152 Q2W 116 Q2W	1/6 1/6	152 Q2W	0.408	0.048
6	152 Q2W 116 Q2W	2/6 1/6	152 Q2W	0.555	0.147
7	152 Q2W 116 Q2W	3/6 1/6	116 Q2W	0.582	0.167
8	152 Q2W 116 Q2W	0/6 0/6	152 QW	0.283	0.058
9	152 Q2W 116 Q2W	1/6 1/6	116 QW	0.519	0.188

Abbreviations: D=number of participants with DLT, N=number of DLT-evaluable participants; mg=milligrams; Pr(TT)=probability of target toxicity; Pr(OD)=probability of overdosing; Q2W=once every two weeks.

CCI

5.2. General Methods

Unless otherwise specified, all efficacy analyses and safety analyses will be performed using the Safety Analysis Set. All analyses will be performed by part as follows:

- Part 1;
- Part 2;
 - Part 2A Dose level 1 (if Dose level 2 is identified as RP2D);
 - Part 2A (RP2D) + Part 2B;
 - CCI
- Part 1 and Part 2 Combined.

5.2.1. Data Handling After the Cutoff Date

Data collected after the cutoff date may not undergo the cleaning process and will not be displayed in any listings or used for summary statistics, statistical analyses or imputations.

5.2.2. Pooling of Centers

In order to provide overall estimates of treatment effects, data will be pooled across centers. The 'center' factor will not be considered in statistical models or for subgroup analyses due to the high number of participating centers in contrast to the anticipated small number of participants randomized at each center.

5.2.3. Analyses to Assess the Impact of COVID-19 Pandemic

The study enrollment may start during the COVID-19 pandemic period. If so, data summaries and analyses may be performed to assess the impact of COVID-19 on the trial population and study data. Details of these summaries and analyses are included in the respective sections.

5.2.4. Definition of Study Day

The study day for assessments occurring on or after the first dose of study intervention (eg, adverse event onset, disease measurement) will be calculated as:

$$\text{Study day} = \text{Date of the assessment/event} - \text{start date of study intervention} + 1.$$

The study day for assessments occurring prior to the first dose of study intervention (eg, baseline characteristics, medical history) will be negative and calculated as:

$$\text{Study day} = \text{Date of the assessment/event} - \text{start date of study intervention}.$$

The study day will be displayed in all relevant data listings.

5.2.5. Definition of Cycle and Cycle Day

Cycle start and end dates are derived per participant. The definition for each cycle is driven by the study intervention elranatamab. Elranatamab is administered in a 28-day cycle.

- For Cycle 1, the actual cycle start date is the date each participant receives the first non-zero study intervention;
- For all other cycles, the actual cycle start date for each participant is the earliest start date of dosing in the Cycle X Day 1 visit CRF exposure page;
- For all but the last cycle:
 - Actual cycle stop date is calculated as the start date of the next cycle minus 1 day;
 - Actual cycle duration is calculated from Day 1 of a cycle to the day prior to Day 1 of the next cycle, as follows:

$$\text{Actual Cycle Duration (weeks)} = (\text{cycle stop date} - \text{cycle start date} + 1)/7$$

- For the last cycle, actual cycle duration is the planned cycle duration and actual cycle stop date is calculated as actual cycle start date + 28 – 1 day.

The cycle day will be calculated as:

$$\text{Cycle day} = \text{Date of the assessment/event} - \text{cycle start date} + 1.$$

5.2.6. Definition of Start of New Anticancer Therapy

Start date of new anticancer therapy (drug, radiation with curative intent) is used to determine the end of the on-treatment period (see [Section 3.5](#)) and for censoring in efficacy analyses (see [Section 6.3.5](#)).

The start date of new anticancer therapy is the earliest date after first dose date amongst the following:

- Start date of anticancer drug therapy recorded in the ‘Next Anticancer Therapy (NXT CNCR)’ CRF page;
- Start date of radiation therapy with curative intent recorded in ‘Concomitant Radiation’ and ‘Non-drug Treatments – Follow up Radiation (NXT RAD)’ eCRF pages;
- Start date of transplant recorded in ‘Transplant details (TRANSPLT)’ eCRF page.

When start date of new anticancer therapy is missing or partially missing, the imputation rules described in [Section 5.3.3.4](#) should be applied using the data collected on the eCRF pages described above.

5.2.7. Date of Last Contact

The date of last contact will be derived for participants not known to have died at the data cutoff date using the latest complete date (ie, imputed dates will not be used in the derivation) among the following:

- All assessment dates (eg, blood draws [safety laboratory, Pharmacokinetics (PK), CCI and immunogenicity], vital signs, physical exam, neurological exam, performance status, ECG, Echocardiograms [ECHO]/multigated acquisition [MUGA] scans, disease assessments, etc.);
- Start and stop dates of concomitant therapies including non-drug treatments or procedures;
- Start and end dates of new therapies administered after study intervention discontinuation including systemic therapy and radiation;
- AE start and end dates;
- Last date of contact collected on the ‘Survival Follow-up’ CRF (do not use date of survival follow-up assessment unless status is ‘alive’);
- Study intervention start and end dates;
- Date of discontinuation on disposition CRF pages (do not use if reason for discontinuation is lost to follow-up or death).

Only dates associated with actual examinations of the participant will be used in the derivation. Dates associated with a technical operation unrelated to participant status such as the date a blood sample was processed or dates when data were entered into the CRF will not be used. Assessment dates after the data cutoff date will not be applied to derive the last contact date.

5.2.8. Disease Assessment Date

The Date of Disease Assessment at each nominal timepoint as provided by the investigator on the IMWG response assessment CRF page will be utilized for the respective analyses.

5.2.9. Adequate Baseline Disease Assessment

Adequate baseline is defined using the following criteria:

- All documented lesions must have non-missing assessments (ie, non-missing measurements for target lesions and meeting criteria for measurable lesions, and non-missing lesions status at baseline for non-target lesions);
- Baseline lesions must be assessed with an acceptable method of tumor assessment as specified in the protocol (eg, PET/CT, CT or MRI);

- Measurable disease based on IMWG criteria as defined by at least 1 of the following:
 - Serum M-protein >0.5 g/dL by SPEP;
 - Urinary M-protein excretion \geq 200 mg/24 hours by UPEP;
 - Serum immunoglobulin FLC \geq 10 mg/dL (\geq 100 mg/L) AND abnormal serum immunoglobulin kappa to lambda FLC ratio (<0.26 or >1.65).

5.2.10. Adequate Post-baseline Disease Assessment

An adequate disease assessment is defined as an assessment where a time-point response of sCR, CR, VGPR, PR, minimal response (MR), Stable Disease (SD) or PD has been provided. Timepoints where the response is not evaluable or no assessment was performed will not be used for determining the censoring date for time-to-event endpoints including PFS, DOR and DOCR.

5.2.11. Nominal and Unscheduled Visits

For all algorithms and analyses, visit labels as specified on the CRF will be used as the nominal timepoint (ie, assessment will not be slotted).

Unless otherwise specified, unscheduled assessments will not be displayed in summary tables by nominal visit/timepoint. Unscheduled assessments will be used when deriving baseline and worst case on-treatment for safety analyses (except where noted for baseline ECGs). Additionally, unscheduled assessments will be used for efficacy analyses (eg, defining date of progression/censoring, best overall response, date of last contact).

5.2.12. Standard Deviations and Reporting Conventions

The following conversion factors will be used to convert days into weeks, months or years:
1 week = 7 days, 1 month = 30.4375 days, 1 year = 365.25 days.

Demographics and physical measurements:

- Age [years]: (year of given informed consent – year of birth). The integer part of the calculated age will be used for reporting purposes.
- Body mass index (BMI) (kg/m^2) = weight (kg)/[height (m)]².

For reporting conventions, mean and median should generally be displayed to 1 more decimal place than the raw data and standard deviation should be displayed to 2 more decimal places than the raw data. Percentages will be reported to 1 decimal place. The rounding will be performed to closest integer/first decimal using the common mid-point between the 2 consecutive values. For example, 5.1 to 5.4 will be rounded to an integer of 5, and 5.5 to 5.9 will be rounded to an integer of 6.

5.2.13. Analyses for Continuous and Qualitative Variables

Continuous variables will be summarized using descriptive statistics ie, number of non-missing values and number of missing values [ie, n (missing)], mean, median, standard deviation, minimum, maximum and first and third quartile (Q1 and Q3).

Qualitative variables will be summarized by frequency counts and percentages. Unless otherwise specified, the calculation of proportions will include the missing category. Therefore, counts of missing observations will be included in the denominator and presented as a separate category.

In case the analysis refers only to certain visits, percentages will be based on the number of participants still present in the study at that visit, unless otherwise specified.

5.2.14. Analyses for Time-to-Event Endpoints

Kaplan-Meier estimates (product-limit estimates) will be presented together with a summary of associated statistics including the median time with 2-sided 95% CIs. Probabilities of an event at particular timepoints will be estimated with corresponding 2-sided 95% CIs. The CI for the median will be calculated according to Brookmeyer and Crowley, 1982⁹ and the CIs for the survival function estimates at particular timepoints will be derived using the log(-log) method.¹⁰

5.3. Methods to Manage Missing Data

Unless otherwise specified, all data will be evaluated as observed, and no imputation method for missing values will be used.

Any imputations will occur at the analysis dataset level. Additionally, in all data listings imputed values will be presented and flagged as imputed.

Missing statistics, eg, when they cannot be calculated, should be presented as ‘ND’ for not done, ‘NR’ for not reached or ‘NA’ for not applicable. For example, if N=1, the measure of variability cannot be computed and should be presented as ‘ND’ or ‘NA’.

5.3.1. Missing Pharmacokinetic Data

Concentrations below the limit of quantification

For all calculations and figures, all concentrations assayed as below the limit of quantification (BLQ) will be set to zero. The BLQ values will be excluded from calculations of geometric means and their CIs. A statement similar to ‘All values reported as BLQ have been replaced with zero’ will be included as a footnote to the appropriate tables and figures. In listings BLQ values will be reported as below limit of quantification (“< LLOQ”), where LLOQ will be replaced with the corresponding value from the analytical assay used.

Deviations, missing concentrations and anomalous values

In summary tables, concentrations will be set to missing if one of the following cases is true:

- A concentration has been reported as ND (ie, not done) or NS (ie, no sample);
- A deviation in sampling time is of sufficient concern or a concentration has been flagged as anomalous by the clinical pharmacologist.

At the discretion of the clinical pharmacologist, summary statistics may not be presented at a particular time point if more than 50% of the data are missing. For analysis of pharmacokinetic concentrations, no values will be imputed for missing data. If less than 3 evaluable concentrations or PK parameters at a given timepoint are available, only minimum and maximum will be presented.

5.3.2. Missing ECG Data

For QTc analyses, no values will be imputed for missing data. If 1 or 2 of the triplicate measurements for an ECG parameter are missed, the average of the remaining 2 measurements or the single measurement, respectively, can be used in the analyses. If all triplicate measurements are missing at a timepoint for an ECG parameter, no values will be imputed for this timepoint. If the triplicate needs to be repeated because of an artifact, then the repeated triplicate will be reported on an unscheduled CRF page. Based on a review of the data, these unscheduled assessments may be used in place of the assessments at the nominal time. Data review and consultation with the study team is required to flag these cases.

5.3.3. Handling of Incomplete or Missing Dates

5.3.3.1. Adverse Events

AE Onset Date: If the AE onset date is completely missing, and if the date of first dose is earlier than AE stop date, then the onset date will be assigned as the date of first dose. Otherwise if the date of first dose is after the AE stop date then the AE onset date will be imputed as the earliest of non-missing AE stop date or informed consent date.

AE Stop Date: If the AE stop date is completely missing then the stop date will be imputed as the latest of the participant withdrawal/completion date, death date, last dose of study intervention, or AE onset date.

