3.4. Baseline Variables

Start and end dates of study intervention:

The date of first dose (start date) of study intervention is the earliest date of nonzero dosing of the study drug.

The date of last dose of study intervention is the latest date of the nonzero dosing of the study drug.

Definition of baseline:

No windowing will be applied when defining baseline. For example, the protocol requires safety assessments to be performed within 28 days prior to first dose; however, values outside this window will not be excluded when determining baseline assessments. Any deviations from the protocol specified window will be documented as protocol deviations. A separate definition of adequate baseline ([Section 5.2.9](#)) is provided for disease assessment related efficacy endpoints.

For all endpoints, the last assessment performed on or prior to the date of the first dose of study intervention will serve as the baseline assessment. If there are no observations meeting these criteria, then baseline is considered missing.

Participants who start treatment and discontinue from the study on the same day may have 2 different sets of data collected on Study Day 1 (one during study and one in the End of Treatment [EOT] visit). Data reported at the EOT visit are not eligible for baseline selection.

Triplicate ECGs are collected at all timepoints except screening (single ECG at screening); therefore, the baseline for ECG measurement is the pre-dose on Cycle 1 Day 1, or the most recent ECG assessment reported prior to the first administration of study drug. Unscheduled assessments will not be included in the calculation of the average. The average of the replicate measurements will be determined after the derivation of the individual parameters at each timepoint.

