5.3.3.2. Exposure

No imputation will be done for first dose date. Date of last dose of study intervention, if unknown or partially unknown, will be imputed as follows:

- If the last date of study intervention is completely missing and there is no End of Treatment (EOT) CRF page and no death date, the participant should be considered to be ongoing and use the data cutoff date for the analysis as the last dosing date; or

- If the last date of study intervention is completely or partially missing and there is either an EOT CRF page or a death date available (on or prior to the data cutoff date), then impute this date as the last dose date:
 - = 31DECYYYY, if only Year is available and Year < Year of min (EOT date, death date);
 - = Last day of the month, if both Year and Month are available and Year = Year of min (EOT date, death date) and Month < the month of min (EOT date, death date); or
 - = min (EOT date, death date), for all other cases.

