6.8.1.1. Adverse Events of Special Interest

Adverse events of special interest (AESI) include the following events:

- CRS: PT coded as “cytokine release syndrome” and collected on the AE CRF page;
- ICANS: PT coded as “immune effector cell-associated neurotoxicity syndrome” and collected on the AE CRF page;
- Peripheral neuropathy: Standardized MedDRA Queries (SMQ) Peripheral Neuropathy (narrow and broad excluding PTs included in the Guillain-Barre syndrome SMQ) and Guillain-Barre syndrome SMQ (narrow).

CRS and ICANS will be assessed according to ASTCT criteria. All the analyses will be performed by each individual AESI separately.

A high-level summary of each AESI will include the number and percent of participants with, separately:

- Any AESI;
- Serious AESI;
- AESI by maximum toxicity grade;
- Had >1 AESI (for CRS and ICANS only);
 - Note: If there are >1 AESI with different grades between the two doses, it will be considered as one AESI.
- Had ICANS concurrent with CRS (for ICANS only). Note: if both CRS and ICANS occurred between the same two doses they will be considered as concurrent;
- AESI leading to dose interruptions;
- AESI leading to dose reductions;
- AESI leading to dose interruptions or reductions;
- AESI leading to permanent discontinuation of study intervention;
- AESI with outcome as resolved (for peripheral neuropathy only).

In addition, the following summary will be provided with descriptive statistics (mean, median, standard deviation, minimum, and maximum) as well as broken down in categories by the time to onset and resolution of the AESI:

- Time to onset of the AESI;

- Time to resolution of the AESI).
- Duration of each AESI event.

For CRS and ICANS, time relative to dose (ie, after the first dose, after the second dose, after >2 doses) will also be summarized with descriptive statistics (mean, median, standard deviation, minimum, and maximum).

A summary of AESI symptoms will be provided as follows. The most severe symptom will be summarized if participants have multiple occurrences of AESI symptoms.

- The CRS symptoms as collected on the ‘CRS AE’ CRF will be summarized by symptom grade using frequency counts and percentages;
- The ICANS symptoms as collected on the ‘ICANS’ CRFs will be summarized using frequency counts and percentages;
- The ICE scores as collected on the ‘ICE’ CRFs will be summarized for those participants with ICANS events based on the total ICE scores as follows:
 - ICE score 10;
 - ICE score 7-9;

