6.8.1.2. Other Adverse Events of Clinical Interest

Other adverse events of clinical interests (oAECIs) include the following events:

- Infections:
 - The MedDRA SOC of Infections and infestations.

- Cytopenias:
 - The MedDRA PTs for cytopenia are defined in the Appendix ([Section 9.1](#)).
- Injection site reactions:
 - The MedDRA HLT of Injection site reactions.
- Hypogammaglobulinemia
 - Including the MedDRA PTs: Blood immunoglobulin G decreased, Hypogammaglobulinaemia, Hypoglobulinaemia, Immunoglobulins decreased and Globulins decreased.

All the analyses will be performed by each individual oAESI separately. For cytopenias, the individual PTs (ie, not clustered terms) will be reported in the summary.

A high-level summary of each oAECI will include the number and percent of participants with:

- Any oAECIs;
- Serious oAECIs;
- oAECIs by maximum toxicity grade;
- oAECIs leading to dose interruptions;
- oAECIs leading to dose reductions;
- oAECIs leading to dose interruptions or reductions;
- oAECIs leading to permanent discontinuation of study intervention;

The following summary will be provided for each oAESI:

- oAECI by PT and maximum severity grade (all causality and treatment-related);
- Time to onset of the oAECI and time to resolution of the oAECI with descriptive statistics (mean, median, standard deviation, minimum, and maximum).

A listing of oAECIs with supportive information will also be provided.

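### The SAP's imputed AE stop date has no exception for ongoing events, so unresolved AEs can enter the uncensored time-to-resolution and duration summaries with an artificial end

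*SAP*

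**What the plan says.** SAP 5.3.3.1 covers any AE whose stop date is completely missing. The date is "imputed as the latest of the participant withdrawal/completion date, death date, last dose of study intervention, or AE onset date". Events recorded as ongoing or not resolved are not mentioned.

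Two other sections determine what last dose means in this rule. SAP 3.4: "The date of last dose of study intervention is the latest date of the nonzero dosing of the study drug". SAP 5.3.3.2, for a participant with neither a death date nor an end-of-treatment page, where the last dosing date is missing: "the participant should be considered to be ongoing and use the data cutoff date for the analysis as the last dosing date".

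SAP 5.3 places imputations in the analysis datasets and flags imputed values in listings. It does not require a flag in summary tables.

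The summaries that depend on a stop date are these:

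- **SAP 6.8.1.1 (CRS, ICANS, peripheral neuropathy):** "Time to resolution of the AESI" and "Duration of each AESI event", by mean, median, standard deviation, minimum and maximum, and "broken down in categories by the time to onset and resolution of the AESI". Peripheral neuropathy alone also has a count of events whose recorded outcome is resolved.
- **SAP 6.8.1.2 (infections, cytopenias, injection site reactions, hypogammaglobulinemia):** "time to resolution of the oAECI with descriptive statistics". There is no duration item and no resolved-outcome count.

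Neither section defines time to resolution, limits it to resolved events, or provides for censoring.

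**The concern.** An AE with no stop date has usually not ended by the time of the analysis. For a time-to-resolution summary that is a censored observation. The rule in 5.3.3.1 turns it into a complete one, and the end date it supplies (death, withdrawal, last dose, or the onset date itself) is not a resolution.

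Two features sharpen this. First, last dose is not the end of observation. Protocol 7.1 keeps following unresolved AEs at least every 4 weeks after treatment ends, until resolution or until no further improvement is expected. Second, under SAP 3.5 events starting up to 90 days after last dose (or until new anticancer therapy starts) are treatment-emergent, so events with onset after last dose belong in the tables.

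At stake is how reversibility is described. Protocol 8.3.8.3 calls peripheral neuropathy an important potential risk. Protocol 2.3.1 says elranatamab likely contributes to worsening hypogammaglobulinemia and neutropenia. Understated times would be wrong in the reassuring direction.

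**Working it through.** The plan states no figure for this rule, so there is nothing to reproduce. The check has two parts.

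**1. The rule applied to an unresolved AE.** Stop = max(withdrawal/completion, death, last dose, onset), using whichever dates exist. Duration = stop − onset + 1. The SAP gives no formula for AE duration; the +1 is assumed by analogy with its other time variables. Days are study days.

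| Situation (event never resolved) | Imputed stop | Duration |
|---|---|---|
| Onset 60, last dose 120, alive in follow-up at 400 | 120 | 120 − 60 + 1 = 61 |
| Onset 60, last dose 120, died 200 | 200 | 200 − 60 + 1 = 141 |
| Onset 60, last dose 120, withdrew 300 | 300 | 300 − 60 + 1 = 241 |
| Onset 60, on treatment, last dose or cutoff 400 | 400 | 400 − 60 + 1 = 341 |
| Onset 150, last dose 120, alive in follow-up | 150 | 150 − 150 + 1 = 1 |

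In the first row the event has been open for at least 400 − 60 + 1 = 341 days but is given 61. In the second, death becomes the end of the event. In the last, an open event becomes a 1-day event.

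**2. Effect on a median, under assumptions.** The documents do not give the fraction of AEs without a stop date. Assume independent exponential times: true time to resolution with median m, and time from onset to the imputed stop with median c. Then:

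- fraction unresolved = m/(m + c)
- median with imputed stops counted as resolutions = m·c/(m + c)

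For m = 90 and c = 60: unresolved 90/150 = 60%, median 5400/150 = 36 days. For m = 90 and c = 240: unresolved 90/330 = 27%, median 21600/330 = 65 days.

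A simulation of 200,000 events per scenario agrees (Kaplan-Meier on 20,000 of them). Medians are in days:

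| m | c | Unresolved | Imputed stops as resolutions | Resolved events only | Kaplan-Meier, unresolved censored |
|---|---|---|---|---|---|
| 30 | 60 | 33% | 20 | 20 | 30 |
| 30 | 240 | 11% | 27 | 27 | 30 |
| 90 | 60 | 60% | 36 | 36 | 90 |
| 90 | 240 | 27% | 65 | 65 | 91 |
| 180 | 60 | 75% | 45 | 46 | 181 |
| 180 | 240 | 43% | 103 | 103 | 178 |
| 365 | 60 | 86% | 52 | 51 | 367 |
| 365 | 240 | 60% | 145 | 145 | 370 |

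With c = 120 the imputed medians lie between the two rows shown for each m. The fifth and sixth columns show that dropping unresolved events is no cure. Short events are the ones seen to resolve, so the resolved-only median is biased to the same extent here.

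**The case against.** A reader might infer that the plan reports unresolved neuropathy, infections and cytopenias as resolved. The documents do not support that. No section says that imputation changes an event's outcome, or expressly that imputed dates feed time to resolution, and the ordinary meaning of the term requires a resolution. Whether an event marked ongoing counts as having a missing date may be settled in CRF or programming specifications that are not available here. For neuropathy, the resolved count uses the recorded outcome and would show how many events remained open.

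Other limits also stand:

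- Duration is planned only for CRS, ICANS and neuropathy, not for the events in 6.8.1.2.
- The imputed date is not only last dose or death. It can be withdrawal/completion, onset or, through 5.3.3.2, data cutoff.
- For an event that did resolve but whose date was lost, taking the latest date tends to lengthen the time. The downward bias concerns unresolved events.
- The documents give no persistence rate for neuropathy or hypogammaglobulinemia, so a claim that they often persist cannot be made from them.
- Imputed values are flagged in listings, and AESI and oAECI listings are planned.

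These points limit the claim but do not remove it. The trigger is any completely missing stop date, the imputation is made in the datasets behind the tables, and nothing keeps the imputed date out of the summaries. For the events in 6.8.1.2 no planned row would reveal the problem.

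**Conclusion.** The concern holds as a defect in secondary descriptive safety summaries. SAP 5.3.3.1, read with 6.8.1.1 and 6.8.1.2, allows unresolved events to be summarised with an artificial end, which understates time to resolution. The most distorted case is an ongoing event starting after last dose in a participant alive in follow-up, which would be given 1 day.

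The size cannot be determined from the documents. The 36 to 65 days against a true 90, and 45 to 103 against a true 180, illustrate direction and possible scale. They rest on assumed exponential, independent times and assumed unresolved fractions of 27% to 60% and 43% to 75%.

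It would be wrong to conclude that the trial's main safety conclusions are affected. The primary endpoint (Grade 2 or higher CRS in Cycle 1) is an incidence, the DLT analysis is a rate, and the enrollment-hold rules count participants with events. None uses an imputed stop date, nor does the neuropathy resolved-outcome count.

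**What to change.** 1. In SAP 5.3.3.1, state that no stop date is imputed for AEs recorded as ongoing or not resolved when time to resolution or duration is derived.
2. In SAP 6.8.1.1 and 6.8.1.2, define time to resolution and report the numbers resolved and unresolved for every AESI and oAECI, not only for neuropathy.
3. Estimate time to resolution by Kaplan-Meier with unresolved events censored at last AE follow-up or data cutoff, or by cumulative incidence with death as a competing event. The second is cleaner where deaths with open events are common, because death precludes resolution. Under either method death must not count as resolution.
4. If descriptive durations are kept, restrict them to resolved events, label them so and treat them as supplementary, since that restriction alone does not remove the bias.

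The cost is SAP wording and routine programming. No new data should be needed: Protocol 7.1 already requires follow-up of unresolved AEs, and SAP 6.8.1.1 already relies on a recorded outcome for neuropathy.
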